For Cohort A Part 1, 60 mg single dose will be administered on Day 1; 120 mg single dose will be administered on Day 3; and then 30 mg dose will be administered BID on Days 6-19. Participants will report to the unit on Day -1 for assessments and randomization (randomization can also be done on Day 1, prior to dosing). Participants will be dosed the following morning on Day 1 followed by post-dose assessments. Blood for PK assessments will be collected for the next 48 hours (h). On Day 3 (after collection of 48 h PK time point), participants will receive a single dose of 120 mg followed by post-dose assessments and PK assessments for the next 72 h. Repeat dosing will begin on the morning of Day 6 (after collection of 72 h PK time point) and will continue for 14 days BID. Participants will remain in the unit for additional 2 days until 72 h PK timepoint is collected. Dosing frequency and duration may be adjusted based on emerging safety and tolerability data. Participants will return for the follow-up visit approximately 30 days after discharge. All male participants will also be called approximately 7 months after the follow-up visit to ensure no partner pregnancy.

For Cohort B Part 1, Repeat Dose SoA will be followed for the duration of the study. Participants will report to the unit on Day -1 for assessments and randomization (randomization can also be done on Day 1, prior to dosing). Dosing will begin on the morning of Day 1 and continue for 14 days BID. Dosing frequency and duration may be adjusted based on emerging safety and tolerability data. BAL procedure will be performed as soon as possible (within 1 h) after the first (morning) dose on one of the following days: 10, 11, 12, or 13. Participants will be discharged on Day 15 following completion of all post-dose assessments after the last dose, or later if additional PK collection or other assessments are required. Participants will return for the follow-up visit approximately 30 days after discharge. All male participants will also be called approximately 7 months after the follow-up visit to ensure no partner pregnancy.

For Cohort C Part 1, 14 healthy participants will be enrolled to evaluate bystander exposure and will follow Cohort C Part 1 SoA. Bystanders and air exposure will be evaluated concomitantly with Cohort B Part 1. Bystanders will report to the unit on Day

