5.5. Dose Justification

The dose proposed for Part 1 Cohort A is based on the data from 202031 where CCI15106-CFI up to 60 mg single dose has been evaluated, and no SAEs or severe AEs were observed, as well as the investigation of the four week toxicity and toxicokinetics in rats and dogs in which the NOAEL was determined [GSK Document Number 2017N312240 00 and GSK Document Number 2017N312247 00].

Table 1 below shows the safety margins in terms of lung and systemic exposure with respect to the NOAEL obtained from the pre-clinical studies, and the folder cover with respect to the systemic exposure following oral administration of the marketed dose (1200 mg/day) in humans for the doses proposed in this study. These data indicated reasonable safety margins for Cohort A in Parts 1 and 2, where single dose of CCI15106-IP will be administered.

The selection of appropriate dose for Part 1 Cohort B will be performed upon consideration of available safety, tolerability and systemic PK data from Part 1 cohort A. The review data set for this selection will, at minimum, consist of: any adverse events, liver function test results, vital signs, ECG, spirometry data, and laboratory findings, and any available systemic PK results.

The selection of appropriate dose for Part 2 Cohort A will be performed upon consideration of available safety and tolerability data following the single doses (60 and 120 mg) in all participants in Cohort A of Part 1.

The selection of appropriate dose for Part 2 Cohort B will be performed upon consideration of available safety, tolerability, systemic PK and lung concentration data from Part 1 Cohort B.

The dose level in any cohort may be titrated up or down based on emerging safety, tolerability, and systemic PK and lung data where available. The maximum dose will not exceed 120 mg per day.

Table 1 Prediction of Human Systemic and Lung Exposure and Safety Margins of CCI15106

Dose Frequency Assume 100%	Proposed human dose per day (mg)	Human Lung Dose (mg/g) on in humar	Lung Safety Margin (Rats)	Lung Safety Margin (Dogs)	Human Systemic expoure AUC(0-24) (ng.h/mL) *	Systemic Safety Margin (Rats)	Systemic Safety Margin (Dogs)	Systemic Safety Margin (human Oral Ribavirin)
SD	60	0.06	12	16				
SD	120	0.12	6	8				
Assume 59% lung deposition in humans								
SD	60	0.04	20	26	552	17	40	92
SD	120	0.07	10	13	1104	8	20	46
BD**	30	0.04	20	26	3080	3	7	16
BD	60	0.07	10	13	6150	2	4	8

Assumptions:

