6.1. Inclusion Criteria

6.1.1. Inclusion Criteria for Healthy Participants and Bystanders

Participants are eligible to be included in the study only if all of the following criteria apply. Rescreening is allowed only if approved by the Medical Monitor.

Age

1. Participant must be 18 to 65 years of age inclusive, at the time of signing the informed consent.

^{*} human systemic AUC(0-24) is predicted from a mechanistic model [Weber, 2017]

^{**} BD - twice daily dosing; AUC(0-24) on Day 14

Type of Participant and Disease Characteristics

- 2. Participants who are overtly healthy as determined by medical evaluation including medical history, physical examination, laboratory tests, and cardiac monitoring.
- 3. A participant with a clinical abnormality or laboratory parameter(s) which is/are not specifically listed in the inclusion or exclusion criteria, outside the reference range for the population being studied may be included only if the investigator (in consultation with the Medical Monitor if required) decide and document that the finding is unlikely to introduce additional risk factors and will not interfere with the study procedures.

Weight

4. Body weight ≥50 kg for males and 45 kg for females and body mass index (BMI) within the range 19 to 31 kg/m² (inclusive) for males and 17 to 31 kg/m² (inclusive) for females

Sex

5. Male OR Female

a. Male participants:

A male participant with female partner of child bearing potential must agree to use contraception as detailed in Appendix 5 of this protocol during the treatment period and for at least 7 months after the last dose of study treatment and refrain from donating sperm during this period.

b. Female participants:

A female participant is eligible to participate if she is not pregnant (see Appendix 5), not breastfeeding, and not a woman of childbearing potential (WOCBP) as defined in Appendix 5.

Informed Consent

6. Capable of giving signed informed consent as described in Appendix 3 which includes compliance with the requirements and restrictions listed in the informed consent form (ICF) and in this protocol.

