10.3.2. Pharmacokinetic Analyses

PK analysis will be the responsibility of the Clinical Pharmacokinetics Modeling & Simulation Department (CPMS) within GSK. Plasma CCI15106 concentration-time data will be analyzed by non-compartmental methods with WinNonlin 5.3 and above. Calculations will be based on the actual sampling times recorded during the study. From the plasma concentration-time data, the following PK parameters may be determined, as data permit: maximum observed plasma concentration (Cmax), time to Cmax (tmax), area under the plasma concentration-time curve [AUC(0-last) and AUC(0-∞) where data

permit for single dose, and AUC(0- τ) for repeat dose], elimination half-life (t1/2), and clearance (CL/F) as data permit.

AUC(0-24), or AUC(0-48), or AUC(0- τ) and Cmax following single and repeat doses may be used for assessment of dose proportionality.

Trough concentration $(C\tau)$ samples collected on the specified days may be used to assess attainment of steady state. To estimate the extent of accumulation after repeat dosing, the observed accumulation ratio (Ro) may be determined.

To estimate the extent of accumulation after repeat dosing, the observed accumulation ratio (Ro) may be determined from Cohorts B of Part 1 and Part 2.

PK data will be presented in graphical and/or tabular form and will be summarized descriptively. A population PK model (POP PK) may be developed with all available data as appropriate and may be reported separately. Further details of the analysis plan and methods will be detailed within the RAP and data analysis plan OR equivalent.

Individual lung ELF concentration data will be summarised, listed and displayed graphically on both linear and semi-logarithmic scales for the Cohorts with available ELF data. Where data permit, the individual lung ELF concentration data may be plotted against the plasma concentration measured prior to BAL sampling.

All pharmacokinetic data will be stored in the Archives, GSK Pharmaceuticals, R&D.

PK exploratory analyses will be described in the reporting and analysis plan. The population PK analysis if conducted, will be presented separately from the main clinical study report.

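### The Day 3 profile in Cohort A Part 1 is not a carry-over-free 120 mg single-dose profile: analysed uncorrected, exactly proportional exposure would show a 120:60 AUC(0-24) ratio of about 2.35 to 2.70 instead of 2.00

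*Protocol*

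**What the plan says.** Section 5.1 of the current protocol fixes the sequence for Cohort A Part 1: "60 mg single dose will be administered on Day 1; 120 mg single dose will be administered on Day 3", followed by 30 mg twice daily on Days 6 to 19. The gap is exact: "On Day 3 (after collection of 48 h PK time point), participants will receive a single dose of 120 mg". Both administrations are called single doses.

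Section 4 makes the single-dose AUC(0-last), Cmax, tmax, AUC(0-∞), half-life and CL/F primary PK endpoints, as data permit. Dose proportionality is exploratory. Section 10.3.2 specifies non-compartmental analysis. For proportionality it names AUC(0-24), AUC(0-48) or AUC(0-τ), "and Cmax following single and repeat doses may be used for assessment of dose proportionality". It mentions no carry-over and no correction. It allows an optional population PK model and leaves further detail to the Reporting and Analysis Plan (RAP), which is not shown.

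Under Section 5.1, PK from the 60 and 120 mg doses is reviewed before Part 2 Cohort A starts, and PK from all Cohort A dosing before Part 1 Cohort B starts.

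Table 1 in Section 5.5 gives the predicted human AUC(0-24). Its footnote dates the twice-daily rows: "BD - twice daily dosing; AUC(0-24) on Day 14".

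**The concern.** A single-dose profile should start from a negligible concentration, or the earlier dose should be taken out. The protocol gives no half-life and no washout rationale for the 48 h gap, but its own exposure predictions show a drug that accumulates strongly. A drug that had largely washed out in 48 h could not accumulate more than five-fold by Day 14.

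The order is fixed, so the residue always adds to the 120 mg profile and never to the 60 mg one. Uncorrected, it raises the Day 3 AUC, lowers apparent CL/F, and makes linear kinetics look more than dose-proportional. Cohort A supplies the only within-participant 60 versus 120 mg comparison and the only planned 120 mg single-dose profile in healthy participants. What is at stake is the validity of those PK conclusions.

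**Working it through.** **Inputs (Table 1, Section 5.5).** The AUC(0-24) in ng.h/mL is the sixth figure in each row, counting the dosing-frequency label as the first entry:
- single 60 mg: 552 ("SD 60 0.04 20 26 552 17 40 92")
- single 120 mg: 1104 ("SD 120 0.07 10 13 1104 8 20 46")
- 30 mg twice daily: 3080 ("BD 30 0.04 20 26 3080 3 7 16")
- 60 mg twice daily: 6150 ("BD 60 0.07 10 13 6150 2 4 8")

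**Reproducing the table.** The systemic margins are the reference AUC divided by the human AUC. For a single 60 mg dose, 9340/552 = 16.9, 22200/552 = 40.2 and 50722/552 = 91.9 (printed 17, 40, 92). For 30 mg twice daily, 9340/3080 = 3.0, 22200/3080 = 7.2 and 50722/3080 = 16.5 (printed 3, 7, 16). The table reproduces. The 92 in the 60 mg row is a safety margin and plays no part below.

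The twice-daily 30 mg row is 60 mg per day: 60 × 0.59 / 1000 = 0.035 mg/g, which rounds to the printed lung dose of 0.04. A total of 30 mg would give 0.02.

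**Linearity.** 1104/552 = 2.00, so the model is dose-proportional and treats the 120 mg dose as if nothing preceded it.

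**Accumulation at equal daily dose.** 3080/552 = 5.58 and 6150/1104 = 5.57.

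**Implied effective half-life, one compartment.** Solve (1 − e^(−336k)) / (1 − e^(−24k)) = 5.58. This gives k = 0.0075/h and a half-life of 0.693/0.0075 ≈ 92 h. Superposing the 28 actual twice-daily doses gives 92.9 h. Treating Day 14 as full steady state gives 84 h.

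**Carry-over, one compartment.** AUC(48-72)/AUC(0-24) after 60 mg = e^(−48k) = 0.70 (0.67 with 84 h). Under exact proportionality the Day 3 AUC(0-24) would be 1104 + 0.70 × 552 ≈ 1490, and the ratio 1490/552 = 2.70.

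**Without the one-compartment assumption.** Let s_j be the AUC in the j-th 24 h after a single dose divided by AUC(0-24), so that s1 = 1 and s1 + … + s14 = 5.58. In the simplest low-carry-over case, part of the exposure vanishes within a day and the rest does not decline: s3 = (5.58 − 1)/13 = 0.352. A search over all mixtures of declining exponentials that meet the constraint gives s3 from 0.351 to 0.698.

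| Quantity under exact proportionality | Carry-over-free | Uncorrected |
|---|---|---|
| 120:60 AUC(0-24) ratio, 2 + s3 | 2.00 | 2.35 to 2.70 |
| Dose-normalised ratio | 1.00 | 1.18 to 1.35 |
| Power-model slope, ln(ratio)/ln 2 | 1.00 | 1.23 to 1.43 |
| 120:60 AUC(0-48) ratio, 2 + (s3+s4)/(s1+s2) | 2.00 | 2.48 to 2.70 |
| Inflation of 120 mg AUC(0-72), (s3+s4+s5)/(2(s1+s2+s3)) | 0% | 28 to 35% |

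Bi-exponential fits with 20 to 60% of AUC(0-24) in a fast phase fall inside this range: ratios of 2.61 down to 2.39, with terminal half-lives from about 124 h to about 1000 h. The direction is upward in every case.

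**Effect of correction.** In the one-compartment case, removing the decaying residue (0.70 × 552 ≈ 386) returns 1104 and a ratio of 2.00. Subtracting the pre-dose level as a constant over 24 h would over-correct slightly, to about 1.94.

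**Repeat-dose route.** With the same k, the residue of the 60 and 120 mg doses adds about 3% to the Day 19 AUC(0-τ) of 30 mg twice daily. A true ratio of 2.00 against 60 mg twice daily on Day 14 of Cohort B would read about 2/1.03 = 1.94.

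**The case against.** The strongest reply is that this is analysis detail for the RAP. The protocol nowhere says uncorrected values will be used, the 24 h and Day 3 pre-dose samples are scheduled, and Section 10.3.2 already allows a population PK model. That stands as far as it goes: the bias is conditional on no correction being made. But the protocol itself fixes the 48 h gap, the dose order, the single-dose label, the non-compartmental method and AUC(0-24) or AUC(0-48) for proportionality. Followed as written, these give biased primary parameters. The population model is optional, and the gate reviews use PK before final reporting.

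Other replies also have force. Proportionality is exploratory, and the repeat-dose AUC(0-τ) route is nearly free of carry-over, although it compares different participants. AUC(0-∞) and CL/F are reported only as data permit; with a 92 h half-life about 58% of the total AUC lies beyond 72 h (e^(−72k) = 0.58), so they may not be reported at all. An individual two-point correction would be fragile: concentration falls only about 16% between 24 and 48 h (1 − e^(−24k)), and with an assumed 10 to 15% error per sample, roughly 10 to 20% of individual slopes would have the wrong sign.

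**Conclusion.** The point holds. The Day 3 profile is not a carry-over-free single-dose profile, and uncorrected non-compartmental analysis would turn a true 120:60 AUC(0-24) ratio of 2.00 into about 2.35 to 2.70. This rests on linear kinetics and the accumulation in Table 1, on a profile that declines as a mixture of exponentials, and on no correction being applied. The 92 h is implied by Table 1 under a one-compartment model; no half-life is printed. The Cmax effect depends on the height of the early peak, which the protocol does not give.

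A reader might infer more than this:
- **A wrong dose decision would follow.** The protocol does not show that. Section 7.2 rests progression on safety and tolerability with PK as appropriate, the Cohort B review also sees 14 days of 30 mg twice daily, and the bias overstates exposure, which errs towards caution.
- **Dose proportionality cannot be assessed.** The repeat-dose comparison remains available.
- **The Day 6 profile is misused as a 30 mg single-dose level.** No section proposes that use.
- **The protocol protects the accumulation ratio by confining it to Cohorts B.** One sentence in Section 10.3.2 names those cohorts, but the sentence before it carries no such limit.

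**What to change.** In Section 10.3.2, state that the Day 3 AUC, CL/F and half-life, and any 60 versus 120 mg proportionality assessment, are derived after removing the decaying residue of the 60 mg dose. This should also cover the PK shown at the Section 5.1 gate reviews. Preferably use a joint superposition or population PK fit of Days 1 to 6; otherwise subtract the residue using a pooled decline rate, not each participant's own 24 h to 48 h slope. Label uncorrected Day 3 values as including carry-over wherever they appear. Name the repeat-dose AUC(0-τ) comparison, 30 mg twice daily on Day 19 against 60 mg twice daily on Day 14, as the supporting proportionality analysis.

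The cost is wording and programming only, because the samples are already scheduled. The downside is some added variance and dependence on the model used for the residue. No change to dose or schedule is proposed.

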5.2. Number of Participants

Approximately 36 healthy participants and approximately 22 participants with COPD will be randomized in this study for dosing.

Evaluable participants will be defined in the Reporting and Analysis Plan (RAP).

Additional participants or cohorts may be enrolled to allow for evaluation of additional dose levels or to increase numbers on prior doses or to increase the number of bystanders. The total number of participants in this study will not exceed 86 and the total number of cohorts will not exceed 7, including the bystander cohort(s).

If participants prematurely discontinue the study, additional replacement participants may be recruited and assigned to the same treatment sequence at the discretion of the Sponsor in consultation with the investigator.

5.3. Participant and Study Completion

A participant is considered to have completed the study if he/she has completed all phases of the study including the last visit.

The end of the study is defined as the date of the last visit of the last participant in the study.

5.4. Scientific Rationale for Study Design

Participants and all site personnel, with the exception of the study pharmacist or designee, will be blinded to participant randomization throughout the study. The GSK study team participating in the dose escalation meetings will review blinded data and will be un-blinded on a need to know basis only if necessary to facilitate review of the safety, tolerability and PK data as appropriate in real time to inform dose escalation decisions. The GSK study team or personnel at any contract research organization that may be involved in data management or in statistics and programming will not reveal the treatment assignments to the site personnel or participants.

In repeat dosing cohorts, CCI15106-IP will be administered for 14 days to mimic the expected duration of treatment in target patient populations.

Inclusion of Bronchoscopy

BAL will be performed on 14 healthy participants (Cohort B Part 1) and 14 participants with COPD (Cohort B Part 2) to evaluate levels of CCI15106 in the ELF. BAL will be performed once, as soon as possible (within 1h) after the first (morning) dose. This will allow assessment of CCI15106 levels at around tmax in the ELF. The timing of BAL in Part 2 Cohort B may be adjusted based on BAL results obtained in Part 1. Available models [Weber, 2017] predict that the level of CCI15106 in the bronchoalveolar fluid following 14 days of 60 mg BID dosing may be achieved above 200 μ M around T_{max} which is above the EC50 for all respiratory viruses including HRV and expected to prevent or minimise the migration of an upper respiratory tract viral infection to the lower respiratory tract. These data will enable a more accurate estimation of the dose to lung exposure ratio and provide valuable information for future dose predictions.

Inclusion of Participants with COPD Cohort

Due to potential exposure differences as a function of COPD-induced lung damage, participants with moderate COPD will be included to aid in dose selection for the future proof of concept studies in participants with COPD. This cohort will also help obtain some safety and tolerability data in this patient population prior to a wider administration in the Proof of Concept study.

Inclusion of Bystander Cohort

Due to known teratogenic potential of CCI15106, we need to evaluate how much of it gets into the environment around the dosing participant to ensure that no potentially pregnant bystanders are put at-risk due to secondary exposure. Participants dosed in the

Cohort used to evaluate environmental and bystander exposure will be dosed outside a negative pressure enclosure. All other participants will be dosed inside the enclosure. When participants dose outside the enclosure, all personnel will leave the room and not re-enter until 15 min after dosing. During this time, participants will be observed through a window in the door.

5.5. Dose Justification

The dose proposed for Part 1 Cohort A is based on the data from 202031 where CCI15106-CFI up to 60 mg single dose has been evaluated, and no SAEs or severe AEs were observed, as well as the investigation of the four week toxicity and toxicokinetics in rats and dogs in which the NOAEL was determined [GSK Document Number 2017N312240 00 and GSK Document Number 2017N312247 00].

Table 1 below shows the safety margins in terms of lung and systemic exposure with respect to the NOAEL obtained from the pre-clinical studies, and the folder cover with respect to the systemic exposure following oral administration of the marketed dose (1200 mg/day) in humans for the doses proposed in this study. These data indicated reasonable safety margins for Cohort A in Parts 1 and 2, where single dose of CCI15106-IP will be administered.

The selection of appropriate dose for Part 1 Cohort B will be performed upon consideration of available safety, tolerability and systemic PK data from Part 1 cohort A. The review data set for this selection will, at minimum, consist of: any adverse events, liver function test results, vital signs, ECG, spirometry data, and laboratory findings, and any available systemic PK results.

The selection of appropriate dose for Part 2 Cohort A will be performed upon consideration of available safety and tolerability data following the single doses (60 and 120 mg) in all participants in Cohort A of Part 1.

The selection of appropriate dose for Part 2 Cohort B will be performed upon consideration of available safety, tolerability, systemic PK and lung concentration data from Part 1 Cohort B.

The dose level in any cohort may be titrated up or down based on emerging safety, tolerability, and systemic PK and lung data where available. The maximum dose will not exceed 120 mg per day.

Table 1 Prediction of Human Systemic and Lung Exposure and Safety Margins of CCI15106

Dose Frequency Assume 100%	Proposed human dose per day (mg)	Human Lung Dose (mg/g) on in humar	Lung Safety Margin (Rats)	Lung Safety Margin (Dogs)	Human Systemic expoure AUC(0-24) (ng.h/mL) *	Systemic Safety Margin (Rats)	Systemic Safety Margin (Dogs)	Systemic Safety Margin (human Oral Ribavirin)
SD	60	0.06	12	16				
SD	120	0.12	6	8				
Assume 59% lung deposition in humans								
SD	60	0.04	20	26	552	17	40	92
SD	120	0.07	10	13	1104	8	20	46
BD**	30	0.04	20	26	3080	3	7	16
BD	60	0.07	10	13	6150	2	4	8

Assumptions:

human: body weight 70 kg, lung weight 1000 g; 100% or 59% inhaled dose into lungs are assumed

59% was predicted from the MPPD for lung deposition of the device

rat: mean body weight 0.244kg, mean lung weight 1.145 g, 10% inhaled dose into lungs;

dog: mean body weight 8 kg, mean lung weight 73.1 g, 25% inhaled dose into lungs.

Rat NOAEL dose = 32.5 mg/kg, AUC=9.34 µg.h/mL (whole study means)

Dog NOAEL dose = 34.2 mg/kg, AUC=22.2 μg.h/mL (whole study means)

Human oral AUC(0-24) =2xAUC0-12=50.722 μg.h/mL (Steady state) [Copegus USPI, 2015]

